**Table 2: Schedule of Events for Cohort 2 (Healthy Subjects)**

Trial Visits	Screening	Sample Collection Day	Follow-Up (Optional)
	V1	V2	V3
Window (days)	-30 to -1	-	10 to 14 days after Day 1
Informed consent	X		
Demographics	X		
Medical and surgical history	X	X	
Inclusion-exclusion criteria	X	X	
Brief physical examination	X	X	
Vital signs a	X	X	
Skin biopsies collection b		X	
Suture removal (if applicable)			X
Adhesive skin tape strip samples c		X	
Skin microbiome samples d		X	
Concomitant medication	X	X	X
Procedural complications evaluation	X	X	X

Abbreviation: V, visit.

Note: Screening and Day 1 can be performed on the same day (if subjects do not have a washout period for any of the medications or procedures listed in the exclusion criterion or lifestyle considerations) and the scheduled assessments on these two days can be completed only once in this case.

a Including height and weight. Height will be measured only at screening.

b Two skin biopsies (4-mm) that include hair follicles will be collected on healthy skin at similar matched areas of subjects with FFA (ie., 1 from frontal area and 1 from occipital scalp area).

c Skin tape strips will be collected on non-hair bearing healthy skin at a similar matched area of subjects with FFA (ie, on the forehead, as close as possible to the frontal scalp area).

d Two skin swab samples for microbiome analysis will be collected on healthy skin at similar matched areas of subjects with FFA (ie, 1 on frontal scalp area and 1 from occipital scalp area).

## 2 INTRODUCTION

### 2.1 Background

#### 2.1.1 Frontal Fibrosing Alopecia

Frontal fibrosing alopecia (FFA) was first described in 1994 and is a type of primary lymphocytic cicatricial alopecia that is often considered a clinical variant of lichen planopilaris (LPP) due to their shared histopathologic features. This variant of LPP is most commonly found in postmenopausal women and is increasing in prevalence. FFA is characterized by the recession of the frontal, temporal, or frontotemporal hairline; the clinical pattern is distinct and usually includes eyebrow hair loss, as well as other associated symptoms. Pruritus, facial papules, eyelash loss, body hair involvement, and trichodynia may also occur in addition to the frontotemporal recession and eyebrow loss classically seen.

Early diagnosis and prompt treatment are critical as FFA is a progressive disorder that can result in permanent hair loss. However, even with aggressive therapy, FFA may progress. There are a limited number of published guidelines for the treatment of FFA and there is no consensus or standard treatment regimen for FFA. Intralesional corticosteroids may achieve some disease stabilization, with associated adverse effects such as pain and skin atrophy, and topical corticosteroids are often not effective. In addition, no therapeutic interventions selectively target cellular or molecular key elements of FFA pathogenesis.

The etiology and pathogenesis of FFA are not completely understood and remain areas of active investigation. The inflammatory cell infiltrate surrounding lesional hair follicles, namely around the bulge and infundibulum, is characterized by an increase in CD8+ GranzymeB+ cytotoxic T cells and plasmacytoid dendritic cells (pDC), with elevated levels of the chemokine receptor CXCR3 expression. The available evidence suggests a key role for interferon (IFN)- $\gamma$  in inducing hair follicle immune privilege (HFIP) bulge collapse and subsequent immune-mediated epithelial hair follicle stem cells (eHFSC) destruction observed in FFA. Therapeutically, bulge immune privilege protection/restoration or neutralizing IFN- $\gamma$  may help to better manage this highly treatment-resistant cicatricial alopecia.

#### 2.1.2 Delgocitinib

Delgocitinib is a novel pan-Janus kinase (JAK) inhibitor. After a cytokine binds to its receptor, the JAK family is activated intracellularly, and promotes growth and activation of a variety of cells (eg, lymphocytes) via phosphorylation of the downstream substrate signal transducer and activator of transcription (STAT). The JAK family is essential for the physiological activity of cytokines and plays a critical role in the pathogenesis of diseases with an immunoinflammatory component.

The JAK-STAT pathway is a promising target for the treatment of disorders with an immunoinflammatory component. Several JAK inhibitors (such as ruxolitinib, baricitinib, and tofacitinib) are in clinical development or are already approved for oral or topical treatment of various chronic inflammatory conditions. Delgocitinib ointment (that was developed by Japan Tobacco In. [JT]) has been approved for topical treatment of children aged 2 years and older and

adults with atopic dermatitis (AD) in Japan and delgocitinib cream has shown promising efficacy in inflammatory skin diseases such as chronic hand eczema and AD.

Based on the nonclinical and clinical data currently available, delgocitinib has the potential to become a novel local-acting, selective immunosuppressive agent suitable for the topical treatment of inflammatory dermatological diseases such as FFA.

### 2.1.3 Trial Rationale

FFA demonstrated significant upregulation of T helper 1/IFN (IFN- $\gamma$ , CXCL9/CXCL10), the JAK-STAT pathway (STAT1, JAK3) and fibrosis-related products (vimentin, fibronectin). The increased expression of IFN- $\gamma$ -inducible chemokines (CXCL9, CXC10, and CXC11) and cognate receptor 3 (CXCR3) in lesional FFA bulge epithelium suggest that the CXCL9/10/11-CXCR3 signaling system plays a major role in attracting the inflammatory cell infiltrate in FFA. Interfering with the JAK-STAT signaling pathway may be a novel approach to suppress aberrant immune responses in patients with FFA.

It is hypothesized that delgocitinib cream 20 mg/g will reduce INF- $\gamma$  driven inflammation in subjects with FFA. In the present trial, the molecular signature changes following topical application of delgocitinib cream 20 mg/g in subjects with FFA will be evaluated. The safety and preliminary efficacy of delgocitinib cream in subjects with FFA will also be evaluated.

## 2.2 Risk/Benefit Assessment

### 2.2.1 Known Potential Risks

A total of 15 clinical trials, 1 with oral delgocitinib (sponsored by JT), 11 with delgocitinib ointment (7 sponsored by JT and 4 sponsored by LEO Pharma A/S), and 3 with delgocitinib cream (sponsored by LEO Pharma A/S), have been completed and 2 clinical trials with delgocitinib cream are currently ongoing (sponsored by LEO Pharma A/S). In total, 54 subjects were dosed orally with delgocitinib (at doses between 1 and 100 mg) and 1635 subjects were exposed topically to delgocitinib ointment (1165 subjects at concentrations between 0.3 and 30 mg/g) or delgocitinib cream (470 subjects at concentrations between 1 and 20 mg/g).

Delgocitinib ointment and delgocitinib cream were well tolerated in the conducted clinical trials and systemic exposure to delgocitinib has been low. No clinical indication of any phototoxic potential was observed for delgocitinib cream when single occlusive application of delgocitinib was followed by light exposure in healthy subjects. Potential risks to humans that could arise from use of delgocitinib cream are local skin infection, and acneiform eruptions, which have been reported in clinical trials with delgocitinib ointment. Only few serious adverse events (SAEs) were reported in the completed clinical trials. Except for one, all SAEs were considered not related to treatment. There was no pattern in the reported preferred terms (PT). The one related SAE was an event of *Kaposi's varicelliform eruption* reported in a JT trial with delgocitinib ointment in Japanese subjects. The subject experiencing this event was hospitalized, and the event was resolved.

Generally, no clinically significant changes in laboratory test values, in systolic blood pressure, diastolic blood pressure, pulse rate, or body temperature were observed in subjects exposed to delgocitinib cream. Lymphocytopenia was observed in oral nonclinical toxicity studies and is considered a potential clinical consequence of systemic levels of delgocitinib. Lymphocytopenia is therefore considered an important potential risk for delgocitinib cream.

Further information related to nonclinical and clinical studies is available in the Investigator Brochure (IB).

### **2.2.2 Known Potential Benefits**

For Cohort 1, it is anticipated that subjects randomized to the active investigational medicinal product (IMP) during the vehicle--controlled treatment period and all subjects continuing into the OLE will see an improvement or a stabilization in their FFA condition as a result of participating in this Phase 2a trial.

For Cohort 2, there are no anticipated benefits for subjects participating in the trial, other than the benefit of medical evaluation at screening and throughout the trial.

Participation in this trial may help generate future benefit for larger groups of patients with FFA.

### **2.2.3 Assessment of Risks and Benefits**

All previous data demonstrated in nonclinical and clinical trials are considered sufficient to expect a positive benefit/risk ratio for the treatment of FFA with delgocitinib cream 20 mg/g, and therefore to initiate this trial.

The risks to subjects in this trial will be minimized by compliance with the eligibility criteria, proper trial design, and close monitoring.

### **2.2.4 COVID-19 Pandemic**

Initiating and conducting clinical trials during Coronavirus Disease 2019 (COVID-19) pandemic, presents numerous challenges. Control measures in place in different regions may impact the ability to adhere to some of the trial procedures described in this protocol. Due to challenges that include but are not limited to participant preferences, site closures, travel restrictions, and quarantines, some modifications to trial conduct during the COVID-19 pandemic may be necessary to ensure trial continuity and safety of the participants and trial staff. Adequate benefit/risk analyses should be applied relative to the completion of study procedures. Recognizing the flexibility required to manage the impact of the pandemic on this clinical trial, additional details may be added to study manual(s) and communicated to the site, as needed.

Taking into account the modifications to trial conduct that could occur to minimize risk related to COVID-19 in this trial, the potential risks to participate in this trial during the pandemic are justified by the anticipated benefits that may be afforded to subjects with FFA.

In addition, it is not believed that treatment with delgocitinib cream will put subjects at an increased risk for viral infections, including SARS-CoV-2. Vaccination for COVID-19 will be

allowed during the study, if needed, without changes in currently planned trial procedures and IMP applications.

### 3 OBJECTIVES AND ENDPOINTS

OBJECTIVES	ENDPOINTS
Primary	
To assess molecular signature changes following topical application of delgocitinib cream 20 mg/g in subjects with FFA	Primary endpoint: 

Change in expression of CXCL9, CXCL10, and IFN-<math>\gamma</math> from baseline to Week 12.

Secondary	Safety endpoint during the vehicle-controlled treatment period: 

Number of TEAEs from baseline to Week 12.

Exploratory	Exploratory safety endpoint: 

Number of TEAEs during the OLE (up to Week 26)

 Exploratory efficacy endpoints during the vehicle-controlled treatment period: 

Change in LPPAI score from baseline to Weeks 4, 8, and 12.

Change in FFASS score from baseline to Weeks 4, 8, and 12.

Change in target area perifollicular erythema score from baseline to Weeks 4, 8, and 12.

Change in target area perifollicular scale score from baseline to Weeks 4, 8, and 12.

Change in pruritus NRS score from baseline to Days 2, 3, 4, 5, 6, 7, 8, and Weeks 4, 8, and 12.

Change in burning sensation NRS score from baseline to Days 2, 3, 4, 5, 6, 7, 8, and Weeks 4, 8, and 12.

Change in pain NRS score from baseline to Days 2, 3, 4, 5, 6, 7, 8, and Weeks 4, 8, and 12.

Proportion of subjects with a 3-point reduction* in pruritus NRS score from baseline to Days 2, 3, 4, 5, 6, 7, 8, and Weeks 4, 8, and 12.

Proportion of subjects with a 4-point reduction* in pruritus NRS score from baseline to Days 2, 3, 4, 5, 6, 7, 8, and Weeks 4, 8, and 12.

OBJECTIVES	ENDPOINTS
	

• Proportion of subjects with a 3-point reduction* in burning sensation NRS score from baseline to Days 2, 3, 4, 5, 6, 7, 8, and Weeks 4, 8, and 12.

• Proportion of subjects with a 4-point reduction* in burning sensation NRS score from baseline to Days 2, 3, 4, 5, 6, 7, 8, and Weeks 4, 8, and 12.

• Proportion of subjects with a 3-point reduction* in pain NRS score from baseline to Days 2, 3, 4, 5, 6, 7, 8, and Weeks 4, 8, and 12.

• Proportion of subjects with a 4-point reduction* in pain NRS score from baseline to Days 2, 3, 4, 5, 6, 7, 8, and Weeks 4, 8, and 12.

• Change in target area hair counts/trichoscopy via fotofinder trichovision from baseline to Week 12.

	Exploratory efficacy endpoints during the OLE: 

• These efficacy outcomes will be measured at scheduled visits after Week 12: LPPAI, FFASS, target area perifollicular scale score, target area perifollicular erythema score, pruritus NRS, burning sensation NRS, pain NRS, and target area hair counts/trichoscopy via fotofinder trichovision.

Abbreviations: CXCL9, chemokine (C-X-C motif) ligand 9; 10, chemokine (C-X-C motif) ligand 10; FFA, frontal fibrosing alopecia; FFASS, Frontal Fibrosing Alopecia Severity Score; INF, interferon, LPPAI, Lichen Planopilaris Activity Index; NRS, Numerical Rating Scale; TEAE, treatment-emergent adverse event.

\* Only subjects with a baseline NRS score  $\geq 3$  will be included in the respective endpoints on proportion of subjects with a 3-point reduction. Only subjects with a baseline NRS score  $\geq 4$  will be included in the respective endpoints on proportion of subjects with a 4-point reduction.

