
After the vehicle-controlled treatment period, subjects will continue into the OLE and will apply delgocitinib cream 20 mg/g BID for 12 weeks.
 

• Cohort 2

- No investigational product will be administered in Cohort 2.

		

Objectives:
		

Primary:
 
The primary objective is:
 

• To assess molecular signature changes following topical application of delgocitinib cream 20 mg/g in subjects with FFA.

		

Secondary:
 
The secondary objective is:
 

• To evaluate the safety and tolerability of delgocitinib cream 20 mg/g following topical application in subjects with FFA during the vehicle-controlled treatment period.

		

Exploratory:
 
The exploratory objectives are:
 

• To evaluate the safety and tolerability of delgocitinib cream 20 mg/g during the OLE.

• To evaluate the preliminary efficacy of delgocitinib cream 20 mg/g following topical application in subjects with FFA.

		

Endpoints:
		

Primary Endpoint:
 

• Change in expression of chemokine (C-X-C motif) ligand 9 (CXCL9), chemokine (C-X-C motif) ligand 10 (CXCL10), and interferon (IFN)-<math>\gamma</math> from baseline to Week 12.

		

Secondary Endpoint:
 

• Number of treatment-emergent adverse events (TEAEs) from baseline to Week 12.

		

Exploratory Endpoints:
		

Exploratory safety endpoint:
 

• Number of TEAEs during the OLE (up to Week 26)

		

Exploratory efficacy endpoints during the vehicle-controlled treatment period:
 

• Change in Lichen Planopilaris Activity Index (LPPAI) score from baseline to Weeks 4, 8, and 12.

• Change in Frontal Fibrosing Alopecia Severity Score (FFASS) from baseline to Weeks 4, 8, and 12.

• Change in target area perifollicular erythema score from baseline to Weeks 4, 8, and 12.

• Change in target area perifollicular scale score from baseline to Weeks 4, 8, and 12.

• Change in pruritus Numerical Rating Scale (NRS) score from baseline to Days 2, 3, 4, 5, 6, 7, 8, and Weeks 4, 8, and 12.

		

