## 7.1 Discontinuation

For Cohort 1, subjects who discontinue the trial after the first dose will be asked, if they agree, to come for a last assessment (ET visit). Subjects who are discontinued for safety reasons may be asked to come for additional follow-up visits, at the investigator's discretion, after the ET visit to ensure appropriate medical care and AEs follow-up.

Subjects who discontinue will not be replaced.

Reasons for discontinuation include the following:

- The investigator decides that the subject should be withdrawn. If this decision is made because of an SAE, the IMP is to be discontinued in that subject immediately and appropriate measures are to be taken. The investigator will notify the sponsor immediately.
- If an application site reaction occurs, the investigator should use his or her best medical judgement as to whether to continue subject's treatment.
- The attending physician requests that the subject be withdrawn from the trial.
- The subject, for any reason, requires treatment with another therapeutic agent that has been demonstrated to be effective for treatment of the trial indication. In this case, discontinuation from the trial occurs immediately upon introduction of the new agent.
- The subject is lost to follow-up. In this case, a reasonable attempt to contact the subject and ascertain his or her status must be made, and these attempts must be documented.
- The subject becomes pregnant at any time during the trial.
- Other: the subject may withdraw from the trial for any other reason, including withdrawal of consent.
- The sponsor or regulatory authorities, for any reason, stop the trial. In this case, all subjects will be discontinued from the trial. The investigator will immediately, on discontinuance of the trial by the sponsor, in its entirety or at a clinical trial site, inform both the subjects and the research ethics board of the discontinuance, provide them with the reasons for the discontinuance and advise them in writing of any potential risks to the health of subjects or other persons.

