Should a subject experience an AE/SAE at any time after the informed consent signature until the end of participation in the trial, the event will be recorded as an AE in the source document and eCRF. The investigator is responsible for appropriate medical care of subjects during the trial. All non-serious AEs will be followed until the last subject's visit, unless additional follow up is required per medical judgment. If an SAE is ongoing at the end of trial, the subject will be followed up until the event is resolved or stable. For SAEs which have stabilized and from which the subject cannot be expected to recover during the trial or the safety follow-up period, e.g. chronic or stabilized conditions, the final outcome at the investigator's discretion should be reported as 'recovering/resolving' or 'not recovered/not resolved'. In addition, a statement detailing why the subject cannot be expected to recover during the trial, e.g. that the SAE has stabilized or is chronic, should be added to the narrative description of the SAE on the SAE form. Follow-up frequency will be performed at the discretion of the investigator.

Whenever possible, clinically significant abnormal laboratory results are to be reported using the diagnostic that resulted in the clinically significant abnormal laboratory results and not the actual abnormal test.

In the event the subject experiences a skin reaction that an allergic contact dermatitis is suspected, the event should be documented as an AE and the medication given, if any, recorded. The subject may be re-challenged using the assigned trial medication (patch test in the back) to confirm or rule out contact dermatitis.

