### 9.3.4 Safety Analyses

#### 9.3.4.1 Vehicle-Controlled Treatment Period

##### Cohort 1:

All safety data, including AEs and SAEs will be presented and tabulated according to the Medical Dictionary for Regulatory Activities (MedDRA) classification. Descriptions of AEs will include the start date, the stop date (if it resolved), the severity and seriousness of the AE, the causality of the AE to IMP, and the outcome. The focus in this protocol will be the number of treatment-emergent adverse events (TEAEs).

Adverse events will be considered in vehicle-controlled treatment period or OLE depending on the onset date – if the AE onset date was before Week 12, the AE will be considered as a vehicle-controlled treatment period AE. If the AE had an onset on or after Week 12, the AE will be considered as an OLE AE.

Reported AEs will be summarized by the number of subjects reporting the events, as well as by System Organ Class (SOC), PT, severity, seriousness, and relationship to IMP. For the summary of AEs by severity, each subject will be counted only once within a SOC or a PT by using the AEs with the highest intensity within each category for each analysis. For the summary of AEs by relationship to IMP, each subject will be counted only once within a SOC or a PT by using the AEs with the greatest reported relationship within each category. For the summary of AEs by relationship to IMP and severity, each subject will be counted only once within a SOC or a PT by using (1) the greatest reported relationship followed by (2) the highest reported intensity.

All information pertaining to AEs noted during the trial will be listed by subject, detailing verbatim, SOC, PT, start date, stop date, intensity, outcome, and relationship to IMP. The AE onset will also be shown relative (in number of days) to the day of IMP administration. Serious adverse events will be tabulated by treatment group, relationship to the IMP, and a reference to the occurrence of the SAEs to the relative day of dosing.

AESIs will be listed. No narratives for AESIs will be written in the study report.

Results from laboratory analyses and vital signs will be tabulated by treatment and visit using descriptive statistics. The value at each visit as well as the change from baseline will be presented descriptively.

Clinically significant changes in laboratory analyses and vital signs, and new findings on local tolerability assessments and physical examination will be recorded as AEs.

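### The only secondary endpoint is a raw number of TEAEs with no time at risk, so unequal early leaving can make it understate the TEAE rate in one arm

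*Combined protocol and SAP*

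**What the plan says.** The Synopsis and Section 3 list one secondary endpoint, "Number of TEAEs from baseline to Week 12". Section 9.3.4.1 makes this number the focus of the safety analysis and also plans a summary at subject level: "Reported AEs will be summarized by the number of subjects reporting the events". Neither is related to time observed.

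Four other provisions bear on the point:
- Section 7.1: "Subjects who discontinue will not be replaced". Subjects who stop after the first dose are invited to an ET visit if they agree, and those stopped for safety reasons may be asked to further visits. Table 1 includes adverse event collection at ET.
- Section 8.5.5: for an event arising at any time from consent "until the end of participation in the trial, the event will be recorded as an AE in the source document and eCRF".
- Section 9.2: the safety set for the vehicle-controlled period holds every dosed subject, so an early leaver stays in the arm. The Synopsis says that missing safety data are not imputed.
- Section 8.5.12: worsening of FFA is an efficacy matter and is not recorded as an adverse event.

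For the open-label extension (OLE), Section 3 counts TEAEs up to Week 26. Section 9.3.4.1 assigns events with onset at or after Week 12 to that period. Section 6.1 puts the last application on the evening before the Week 24 visit.

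**The concern.** A count of events depends on the event rate and on how long subjects are watched. A subject who leaves at Week 4 supplies 4 of the 12 planned weeks but is analysed alongside completers without any adjustment. If leaving is uneven, the two counts rest on different amounts of observation, and a reader comparing them has no denominator with which to see it.

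Uneven leaving is foreseeable. Under Section 7.1, starting another agent known to be effective for the trial indication ends participation at once. A subject who leaves for lack of effect therefore loses time at risk without adding a TEAE, because worsening FFA is not recorded as one. If that happens more often on vehicle, the vehicle count falls and the active cream looks worse by comparison. The problem can therefore work against the product as well as for it.

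With about 15 subjects per arm and no test, the table of counts is what readers will compare.

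**Working it through.** The plan states no figure for this endpoint, so there is none to reproduce. Its power statement concerns gene expression and does not bear on TEAEs.

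**Inputs.** About 30 subjects randomised 1:1 (Section 6.3), so n = 15 per arm; 12-week controlled period (Section 4.1). The TEAE rate and the numbers and times of leavers are assumptions.

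**Formulae.** With L leavers at week t, subject-weeks = (15 − L) × 12 + L × t. Expected count = rate per subject-week × subject-weeks. With no leavers, subject-weeks = 15 × 12 = 180.

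**Case 1: leaving unrelated to TEAEs, equal true rates.** Assume 1 TEAE per subject per 12 weeks in both arms and no leavers in the comparison arm (expected count 180/12 = 15.0).

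| Leavers in one arm | Subject-weeks | Expected count | Ratio to 15.0 |
|---|---|---|---|
| 1 at Week 6 | 14 × 12 + 6 = 174 | 14.5 | 0.967 |
| 3 at Week 6 | 12 × 12 + 18 = 162 | 13.5 | 0.900 |
| 3 at Week 4 | 12 × 12 + 12 = 156 | 13.0 | 0.867 |
| 5 at Week 4 | 10 × 12 + 20 = 140 | 11.7 | 0.778 |

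The shortfall runs from 3% to 22%. It equals the lost share of subject-weeks and does not depend on the assumed rate. Per 100 subject-weeks, both arms show 100/12 = 8.33. Equal counts would conceal a true rate ratio of 180/156 = 1.15 with 3 leavers at Week 4, or 180/140 = 1.29 with 5.

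The subject-level summary does not cure this. With Poisson events and 3 leavers at Week 4, the expected proportion with at least one TEAE is [12 × (1 − e^−1) + 3 × (1 − e^−1/3)]/15 = 56.2%, against 1 − e^−1 = 63.2%.

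**Case 2: each leaver leaves because of one extra TEAE.** Three leavers at Week 4, with 156 against 180 subject-weeks.

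| Background TEAEs per subject per 12 weeks | Counts | Difference | Rates per 100 subject-weeks | Difference |
|---|---|---|---|---|
| 0.5 | 6.5 + 3 = 9.5 vs 7.5 | +27% | 6.09 vs 4.17 | +46% |
| 1 | 13.0 + 3 = 16.0 vs 15.0 | +7% | 10.26 vs 8.33 | +23% |
| 2 | 26.0 + 3 = 29.0 vs 30.0 | −3% | 18.59 vs 16.67 | +12% |

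A Week 4 leaver forfeits 8 weeks, so the count falls below the other arm's only if the background exceeds 1/8 = 0.125 per subject-week, which is 1.5 per 12 weeks. In every row the count understates the difference in rates by the same factor, 180/156.

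**OLE window.** Weeks 12 to 26 make 14 weeks, about 2 of them after the last application.

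**The case against.** A reader might infer that the arm with more early leavers will look safer. The documents do not support that. A TEAE that drives a subject out before Week 12 has its onset in the controlled period and is counted, and the second table shows that the arm can then look worse. The claim that stands is that the count can understate the rate in that arm.

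A reader might also infer that nothing is captured once a subject stops. The ET visit and the optional safety follow-up in Section 7.1 are aimed at such subjects. They are voluntary and do not restore observation to Week 12.

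Much of the raw material is already planned. Section 9.3.4.1 lists every event with its dates and its onset relative to dosing, and Section 9.3.6 gives disposition and a list of those who discontinued. Uneven leaving would be visible to someone who worked through the listings, but not in the summary tables.

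Safety is descriptive, so no test or decision rule is biased, and chance variation is larger than the effect. With Poisson counts of 13.0 and 15.0, the gap is 2.0 and the standard deviation of the difference is √28 = 5.3. This limits the importance of the point without removing it.

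Section 9.3.1 leaves safety variable definitions and missing-value handling to a separate SAP. That SAP is not in the text reviewed and may already provide rates.

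Finally, a reader might infer that OLE and controlled-period counts will be set against each other. No section plans this: they are separate endpoints, and the Week 26 limit is stated openly.

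**Conclusion.** The point holds as a modest improvement in reporting. The sole secondary endpoint is a bare count, and the protocol text gives it no denominator in time. If leaving is uneven, the count can understate the TEAE rate in the arm with more leavers, whichever arm that is.

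On assumed figures, the expected count is about 3% to 22% too low when leaving is unrelated to TEAEs. When each leaver has one causative TEAE, a 23% excess in rate appears as a 7% excess in count at a background of 1 per subject. These sizes rest on 15 per arm, a constant background rate, no leavers in the other arm, and 1 to 5 leavers at Week 4 to 6. If leaving is balanced or rare, the distortion largely disappears.

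**What to change.** In Sections 3 and 9.3.4, report for each arm in the controlled period:
- the number of TEAEs;
- the number and percentage of subjects with at least one TEAE;
- subject-weeks at risk, from first dose to the earlier of Week 12 or end of participation;
- TEAEs per 100 subject-weeks.

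Do the same for the OLE, by randomised group and overall, and show events from Week 12 to the last dose (about Week 24) separately from those in the off-treatment follow-up to Week 26. Put the time-at-risk definition in the separate SAP before database lock.

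The cost is a few table columns and some SAP wording. Event dates, clinic dosing dates and discontinuations are already recorded, and no visit, procedure or sample size changes. With about 15 subjects per arm the rates will be unstable, so they belong beside the counts rather than in place of them, and without a test.
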